1. VERSION HISTORY

This Statistical Analysis Plan (SAP) for study MDV3100-18 is based on the Protocol Amendment #2 dated 08-DECEMBER-2016.

 Table 1.
 Summary of Major Changes in SAP Amendments

| SAP Version | Change | Rationale |
|-------------|----------------|----------------|
| 1.0 | Not Applicable | Not Applicable |

2. INTRODUCTION & STUDY DESIGN

This SAP provides detailed methodology for summary and statistical analyses of the data collected in study MDV3100-18. This document may modify the plans outlined in the protocol; however, any major modifications of the primary endpoint definition or its analysis will also be reflected in a protocol amendment. Any deviations from this analysis plan will be described in the Clinical Study Report (CSR).

MDV3100-18 is a phase 2, open-label, single-arm trial of enzalutamide in adult male patients who are chemotherapy-naïve, and who have bone-metastatic castration-resistant prostate cancer.

In this study, approximately 20 adult male patients (age ≥ 18 years) will be enrolled across 3 sites in the United States. The primary objective is to evaluate F-NaF PET/CT imaging as a method for assessing treatment response in metastatic bone lesions either at time of disease progression, or after 2 years of treatment, whichever comes first.

The primary analysis will include all data up to a data cutoff date which will be determined when all patients have progressed or have otherwise been followed for two year or are no longer being followed due to withdrawal of consent, lost to follow-up, or death. All summaries and analyses will include all data pertaining to visits/assessments (both planned and unplanned) performed up to and including the data cutoff date.

[figure not shown]
2.1. Study Objectives

Primary Objectives:

• To evaluate F-NaF PET/CT imaging as a method for assessing treatment response in metastatic bone lesions either at time of disease progression, or after 2 years of treatment, whichever comes first.

Secondary Objectives:

• To evaluate the heterogeneity of response in metastatic bone lesions at the time the primary objective is assessed.

2.2. Study Design

This is a phase 2, open-label, single-arm trial of enzalutamide in adult male patients who are chemotherapy-naïve, and who have bone-metastatic castration-resistant prostate cancer.

In this study approximately 20 adult male patients will be enrolled across 3 sites in the United States. Eligible patients must have bone metastatic disease in at least 2 lesions with a PSA \geq 2 ng/mL. Patients must not have received any prior chemotherapy previously.

Following screening, enrolled patients will have baseline 18F-NaF PET/CT imaging (NaF-1) and then begin open-label treatment with enzalutamide. PSA response will be determined at week 13 when a second 18F-NaF PET/CT imaging (NaF-2) is obtained. Patients with any increase in PSA at week 13 may discontinue treatment and proceed to safety follow-up unless the investigator considers continuation of study drug to be beneficial. For all continuing patients, PSA will be monitored every 8 weeks after week 13 and other study assessments will continue to be obtained. A third 18F-NaF PET/CT imaging (NaF-3) and a follow-up 99mTc-MDP bone scintigraphy will be performed when PSA progression (an increase of at least 25% AND an absolute increase of at least 2.0 ng/mL above nadir), radiographic progression (bone or soft tissue), or other clinically relevant progression (eg, significant bone pain or a skeletal-related event) is observed, or at 2 years without progression after initiation of treatment. No 99mTc-MDP bone scintigraphy will be required at the time the NaF-3 bone scan is obtained if bone disease progression was confirmed earlier on bone scintigraphy obtained at investigator discretion.

Total study duration will be approximately 36 months.

[figure not shown]
Enzalutamide will be administered one daily at a starting dose of 160mg/day. Dose modifications downwards are possible to either 120 or 80 mg/day, per protocol section 6.2.4.

Study periods include screening, treatment, and safety follow-up. Safety follow-up applies to patients who are off protocol therapy and continues to the earliest of 1) 30 days after last dose, 2) death, 3) lost to follow-up, 4) withdrawal of consent, or 5) enrollment into another anti-cancer clinical trial.

The study schematic is provided in Figure 1.

Figure 1. Study Schematic

3. ENDPOINTS AND BASELINE VARIABLES: DEFINITIONS AND CONVENTIONS

Standardized uptake value (SUV) is a unitless measure derived from the imaging PET/CT scans as a ratio of image-radioactivity concentration to the whole-body concentration. SUV and its various uptake measures described below will be analyzed at the central vendor and provided to the sponsor.

For a particular lesion (n), where n = 1, 2, 3, ... N, a 3-dimensional volume of interest (VOI) will be analyzed. Within that VOI for that lesion, there are numerous voxels which compromise the volume. These voxels are 3-dimensional analogs of the 2-dimensional pixels. A particular voxel will be voxel (k), and there are K voxels compromising the entire VOI for that lesion, where k = 1, 2, 3, ... K. Let SUV_k be the SUV for a voxel (k) within that particular lesion.

- **SUV(total)** is the total standardized uptake value. This measure assesses the total tumor burden.
 - First, each lesion (n) of interest produces its own SUV(total) by summing from k=1 to k=K of SUV_k.
 - Second, the sum from n=1 to n=N of each lesion's SUV(total) will produce the desired SUV(total).

- SUV(mean) is the mean standardized uptake value.
 - First, each lesion (n) of interest produces its own SUV(mean) by summing from k=1 to k=K of SUV_k and then dividing that sum by K.
 - Second, the mean from n=1 to n=N of each lesion's SUV(mean) will produce the desired SUV(mean).
- SUV(max) is the maximum standardized uptake value.
 - First, each lesion (n) of interest produces its own SUV(max) by taking the maximum value from k=1 to k=K of SUV_k.
 - Second, the maximum from n=1 to n=N of each lesion's SUV(max) will produce the desired SUV(max).
- **SUV(hetero)** is the heterogeneity measure of tumor activity across all lesions
 - First, each lesion (n) of interest produces its own SUV(mean) by summing from k=1 to k=K of SUV_k and then dividing that sum by K.
 - Second, that lesion's mean is subtracted from the SUV(mean) above, and that difference is then squared.
 - Third, those squared differences from n=1 to n=N are then summed, and then divided by N to produce the desired **SUV(hetero)**.

3.1. Primary Endpoint

The single primary endpoint is the **proportion of patients with** \geq 1 **responding bone lesion on the third scheduled F-NaF PET/CT scan** for this study. For clarity going forward, this scan will be referred to as NaF. Three such NaF scans are scheduled and are noted below:

| Scan identifier | Scheduled to occur at |
|-----------------|--|
| NaF-1 | Screening |
| NaF-2 | Week 13 |
| NaF-3 | Time of progression, or at 2 years after |
| | treatment start, whichever occurs first* |

* If progression occurs before Week 13, then NaF-3 will constitute the scan at progression and support the primary analysis, even though NaF-2 hadn't occurred yet.

A lesion is considered responding if the change from baseline in total standardized uptake value (SUV(total)) is below the limit of agreement (LOA). The LOA will be estimated based upon test/retest analysis and provided by the vendor.

Protocol MDV3100-18 (C3431012) (Enzalutamide) Statistical Analysis Plan

The NaF-3 will be triggered by the earliest of any of the following events:

- Prostate-specific antigen (PSA) progression:
 - Defined as percentage change from baseline $\geq 25\%$ and nominal increase ≥ 2.0 ng/mL above the nadir (or above the baseline if no decline by week 13).
- Bone disease progression:
 - Defined as ≥ 2 new lesions assessed by bone scintigraphy.
- Soft tissue disease progression:
 - Defined by RECIST v1.1.
- Clinically relevant progression:
 - Defined by the investigator.
- Two years after start of therapy.

[figure not shown]
NaF scans will be interpreted by a central imaging vendor.

3.2. Secondary Endpoints

[figure not shown]
There is one secondary endpoint for this study, namely **the heterogeneity of response across all bone lesions at the time the primary endpoint is assessed, SUV(hetero)**. At the NaF-3, the observed SUV(hetero) will be assessed.

3.4. Baseline Variables

The date of first dose (start date) of study treatment is the earliest date of non-zero dosing of the study drug. The date of last dose of study treatment is the latest date of non-zero dosing of the study drug.

No windowing will be applied when defining baseline. Any deviations from the protocol specified window will be documented as protocol deviations. For efficacy analyses and baseline characteristics associated with tumor assessments, the last assessment prior to the date and time of first study drug will serve as the baseline assessment.

For safety, the last assessment performed on or prior to date of the first dose of study treatment will serve as the baseline assessment. If there are no observations meeting these criteria, then baseline is considered missing.

Post-baseline value is defined as a measurement taken after the first administration of study drug. Change from baseline is defined as (post baseline value – baseline value). Percent change from baseline is defined as [(post baseline value – baseline value)/(baseline value)] multiplied by 100%. Both date and time of study drug administration and measurement will be considered when calculating baseline value. If time is not available, then date only will be used.

3.5. Safety Endpoints

Safety endpoints will be summarized based on the on-treatment period unless otherwise specified.

On-treatment is defined as the period between the first dose of the study drug to the earliest of 30 days after the last dose of study drug treatment, the start of cytotoxic chemotherapy, the start of a lutamide (bicalutamide, nilutamide, or flutamide), or the start of a new investigational therapy. Adverse events occurring on the same day as the first dose of study treatment will be considered to have occurred during the on-treatment period. All other assessments which occur on the same day as the first dose of study treatment will be considered.

[figure not shown]
Safety data collected outside the on-treatment period as described above will be listed but not summarized.

An adverse event is considered treatment emergent relative to a given treatment if:

- the event occurs for the first time during the on-treatment period and was not seen prior to the start of treatment, or
- the event was seen prior to the start of treatment but increased in severity during the on-treatment period.

Adverse events will be coded to preferred term and system organ class using the Medical Dictionary for Regulatory Activities (MedDRA) and classified by severity using the CTCAE, version 4.

Hematology and chemistry results will be programmatically graded according to the NCI CTCAE version 4 for relevant parameters. Parameters which cannot be graded will be summarized relative to the normal range (ie, normal range high or normal range low). Additional details are provided in Section 6.6.

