Duration of Treatment: Patients will receive enzalutamide treatment daily as defined in Methods. After NaF-3 is completed, another therapy may be added to enzalutamide as long as it is not another androgen receptor inhibitor, cytotoxic chemotherapy, or an investigational drug. Patients may continue to receive treatment with enzalutamide for as long as the investigator considers it beneficial.

Statistical Methods:

The study endpoints are as follows:

Primary:

- The proportion of patients with at least 1 responding bone lesion (defined as a lesion with a total standardized uptake value [$\text{SUV}_{\text{total}}$] less than that at baseline) on the third ¹⁸F-NaF PET/CT [NaF-3] scan performed for each patient. This assessment will be triggered by disease progression (as defined in Methods) or at 2 years without progression after treatment initiation.

Secondary:

- The heterogeneity of response across all bone lesions as determined by the global heterogeneity of NaF standardized uptake value ($\text{SUV}_{\text{hetero}}$) when the primary endpoint is determined for each patient

CCI

CCI

The primary efficacy endpoint analysis will include patients who undergo at least NaF-1 and NaF-3 ¹⁸F-NaF PET/CT imaging. Definitions of the NaF uptake measures are as follows:

- SUV_{total} Total NaF uptake, which represents the tumor burden across all (global) bone lesions or in individual lesions
- SUV_{hetero} Heterogeneity of NaF uptake, which represents heterogeneity of lesion activity
- SUV_{mean} Mean NaF uptake, which represents the average activity of all lesions
- SUV_{max} Maximum NaF uptake, which represents the activity of the most aggressive lesion
- N Total number of lesions, which represents a numerical sum of all lesions
- VF Volume fraction, which represents the fraction of skeletal involvement

The global SUV_{hetero} score is a measure of the heterogeneity of tumor activity across all bone lesions and is defined as follows, where g = global, l = lesion, N = number of bone lesions.

$$gSUV_{hetero} = \frac{\sum_{i=1}^N (lSUV_{mean}^i - gSUV_{mean})^2}{N}$$

In other words, the global SUV_{hetero} score is the sum of the squares of the differences between the SUV_{mean} for each bone lesion and the global SUV_{mean} , divided by the number of lesions. Thus, a higher global SUV_{hetero} score reflects more heterogeneity in bone lesion activity.

CCI

Circulating tumor cells:

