7.2 Concomitant Therapy

Concomitant medications (including LHRH analogue therapy) will be assessed at all clinic visits. All concomitant medications, including analgesic medications and opiates (including opioid-containing medications), must be recorded on the appropriate case report form. If the use of any medication during the study is due to an adverse event, the adverse event must be recorded on the adverse event case report form and in the patient's source documents.

Initiation of bisphosphonates or denosumab for any reason is prohibited following enrollment; however, treatment with these agents may continue if initiated at least 4 weeks before enrollment. Standard of care supplementation with calcium and vitamin D is encouraged.

The following are prohibited during this study before NaF-3:

- Initiation of cytotoxic chemotherapy

- Radium Ra 223 dichloride or other bone-targeting radionuclide therapy
- Other hormonal therapy, including but not limited to commercially available enzalutamide (Xtandi), abiraterone acetate, androgen receptor inhibitors, 5-alpha reductase inhibitors, or (if for prostate cancer) aminoglutethimide, ketoconazole, or systemic corticosteroids for prostate cancer
- Biologic therapy (other than LHRH analogue therapy)
- Radiation therapy to bone
- Participation in another interventional clinical study of an investigational agent

Another therapy may be used in combination with enzalutamide after NaF-3 with the approval of the investigator and sponsor, except for cytotoxic chemotherapy, antiandrogen therapy (eg, bicalutamide, nilutamide, or flutamide), or another investigational agent. Study drug treatment must be permanently discontinued and patients will have safety follow-up before initiation of one of these prohibited treatments.

The following treatments are allowed:

- Blood transfusions and growth factor support per standard of care and institutional guidelines
- Corticosteroids for indications other than prostate cancer
- Pain therapy per standard of care and institutional guidelines

Deviation from these guidelines should occur only if it is absolutely necessary for the well-being of the patient and does not jeopardize the analysis of the study endpoints, and must follow discussion and agreement between the investigator and the medical monitor, who will determine the patient's suitability for continued treatment with study drug.

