8.3.2.1 Adverse Event Reporting Periods

Collection and reporting of adverse event information will begin at the time the patient signs informed consent for serious adverse events and from the first dose of study drug for nonserious adverse events, and will continue through 30 days after the last dose of study drug treatment or before initiation of cytotoxic chemotherapy, a lutamide (bicalutamide, nilutamide, or flutamide), or a new investigational therapy, whichever occurs first. Additional reporting instructions for serious adverse events and events of special interest are provided in [Section 8.3.5](#).

All adverse events from the time of the first dose of any study drug treatment must be documented on the adverse event case report form and in the patient's clinical record. Any event occurring during screening must be documented on the medical history case report form and in the patient's clinical record for any patient who subsequently meets eligibility criteria and proceeds to treatment.

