10.4 Safety Analyses

All safety analyses will be performed using the safety population.

Safety analyses will be summarized. Safety will be evaluated by the incidence of serious adverse events, incidence and severity of adverse events, incidence of permanent treatment discontinuation due to adverse events, and incidence of new clinically significant changes in clinical laboratory values and vital signs.

The treatment-emergent period is defined as the duration of time from the date and time of the first dose of study drug treatment (enzalutamide) through 30 days after the last dose of study drug treatment (permanent treatment discontinuation) or the day before initiation of cytotoxic chemotherapy, a lutamide (bicalutamide, nilutamide, or flutamide), or a new investigational therapy, whichever occurs first.

Adverse events will be coded according to the Medical Dictionary for Regulatory Activities (MedDRA) and tabulated by system organ class and by preferred term within each system organ class. Tabular summaries will include the incidence overall (number and percentage of patients with treatment-emergent adverse events classified by system organ class and preferred term); incidence by intensity (severity graded according to the CTCAE, version 4), causality, seriousness, and outcome (eg, leading to discontinuation of study drug); and other presentations as appropriate.

Serious adverse events occurring before study treatment will be tabulated separately if considered related to study procedure.

Patients with the same adverse event reported more than once will be counted once at the maximum severity or strongest relationship to study drug.

Toxicity for laboratory parameters (hematology, serum chemistry) will be graded using the CTCAE, version 4 when applicable. Shift tables will be provided as appropriate for each parameter to summarize baseline toxicity grade versus postbaseline toxicity grade. For each laboratory parameter that is not gradable by the CTCAE, a shift table based on the normal range (low, normal, and high) will be provided to summarize baseline result versus postbaseline result. For each laboratory parameter, the baseline laboratory value is defined as the last laboratory value collected on or before the date of the first dose of study drug.

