6.6.1. Adverse Events

Adverse events will be coded using MedDRA, in accordance with the version(s) documented in the data management plan. Adverse events will be graded by the investigator using the CTCAE v4.0.

[figure not shown]
All analyses will be based on treatment emergent events unless otherwise specified. Treatment emergent is defined in Section 3.5. AEs not considered treatment emergent will be flagged in data listings. Only TEAEs with onset date to the earliest of 30 days after the last dose of study drug treatment, the start of cytotoxic chemotherapy, the start of a lutamide (bicalutamide, nilutamide, or flutamide), or the start of a new investigational therapy (whichever occurs first) will be included in the adverse event summaries.

Adverse event incidence will be summarized with frequency and percentage using MedDRA. Some summaries are by system organ class (SOC) and preferred term (PT), while others are only by PT (see below). In addition, adverse event incidence will also be summarized by severity and relationship to study drug. The denominator for the adverse event incidence will be based on the number of patients in the AT population unless otherwise specified.

Patients with multiple occurrences of events for a given preferred term (even if concurrent), system organ class, or overall will only be counted once at the worst severity and strongest relationship to study drug for each preferred term, system organ class, and overall, respectively. If relationship to study drug is missing, the adverse event will be counted as treatment-related. Adverse event listings will show missing relationship as missing.

Tabular summaries including numbers and percentages of the following adverse events will be provided:

- TEAEs;
- TEAEs by SOC and PT;
- TEAEs by PT and maximum severity;
- TEAEs (treatment related);
- TEAEs (treatment related) by SOC and PT;

- TEAEs (treatment related) by PT and maximum severity;
- TEAEs leading to study drug discontinuation by PT;
- TEAEs leading to temporary study drug interruptions by PT;
- TEAEs leading to dose interruptions or reductions by PT;
- Serious TEAEs;
- Serious TEAEs by SOC, PT and maximum severity.

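### The all-causality TEAE tables pool events that occur after another anticancer therapy is added to or follows enzalutamide, with no split at the date that therapy starts

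*SAP*

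**What the plan says.** **When the window closes.** SAP 3.5 gives the definition: "On-treatment is defined as the period between the first dose of the study drug to the earliest of 30 days after the last dose". The remaining closing events are "the start of cytotoxic chemotherapy, the start of a lutamide (bicalutamide, nilutamide, or flutamide), or the start of a new investigational therapy". SAP 6.6.1 repeats the rule for the adverse event tables: "Only TEAEs with onset date to the earliest of 30 days after the last dose of study drug treatment, the start of cytotoxic chemotherapy". Protocol 10.4 lists the same closing events but puts the last day one day earlier for the three therapy classes: "or the day before initiation of cytotoxic chemotherapy, a lutamide".

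**What may be added.** The protocol synopsis, under Duration of Treatment, says "After NaF-3 is completed, another therapy may be added to enzalutamide as long as it is not another androgen receptor inhibitor", and also excludes cytotoxic chemotherapy and investigational drugs. Protocol 7.2 agrees: "Another therapy may be used in combination with enzalutamide after NaF-3 with the approval of the investigator and sponsor", with chemotherapy, antiandrogens and investigational agents excepted. For the excepted classes it adds: "Study drug treatment must be permanently discontinued and patients will have safety follow-up before initiation of one of these prohibited treatments".

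**What is still collected and tabulated.** Protocol 5.2.5 continues the 8-weekly visits, with adverse event review, until permanent discontinuation. SAP 2 summarizes everything up to the data cutoff, with no cut at NaF-3.

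**The concern.** The three therapy classes in the closing list have the effect of keeping other cancer drugs' toxicity out of the study-drug tables. The list does not cover therapies the protocol permits alongside enzalutamide after NaF-3. Protocol 7.2 bars radium Ra 223 and abiraterone before NaF-3 and names neither among the classes barred afterwards.

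Add-on therapy is plausible in this design. NaF-3 is normally triggered by progression, and Protocol 3.5 itself observes that new treatments commonly begin at that point. Patients may stay on enzalutamide for as long as the investigator sees benefit.

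The study has one arm, so no comparator can reveal the contribution of an added agent. A patient is counted once at worst severity (SAP 6.6.1), so a single event attributable to the added agent can determine that patient's cell. The readable SAP has no table that separates this time. Section 6.4 plans no subgroups, 6.5.4 covers only radiotherapy and surgery, and 6.5.6 tabulates concomitant drugs by class and name without relating them to event dates.

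**Working it through.** The plan states no figure on this point, and the sample size of about 20 is a practical choice (Protocol 10.6). The check is a comparison of texts followed by illustrative sizing.

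**Step 1: closing events against permitted therapy.**

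| Therapy | May be combined with enzalutamide after NaF-3 (synopsis; Protocol 7.2) | Closes the window (SAP 3.5, 6.6.1; Protocol 10.4) |
|---|---|---|
| Cytotoxic chemotherapy | No | Yes |
| Lutamide | No | Yes |
| Investigational agent | No | Yes |
| Other anticancer therapy | Yes, with approval | No |

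The last row is the gap. It also covers an unlisted anticancer therapy started after enzalutamide stops but within the following 30 days.

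**Step 2: are the events captured?** Yes. Under Protocol 8.3.2.1, collection "will continue through 30 days after the last dose of study drug treatment or before initiation of cytotoxic chemotherapy" or the other two listed classes, so an unlisted therapy does not stop it.

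**Step 3: how much follow-up could be involved?** Take day 85 as week 13, so 85/30.4375 = 2.8 months. The share of time on drug that falls after NaF-3 is (end − NaF-3 time)/end:

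| Enzalutamide until (assumed) | NaF-3 at 2.8 months | at 12 months | at 24 months |
|---|---|---|---|
| Month 24 | 88.4% | 50.0% | – |
| Month 36 | 92.2% | 66.7% | 33.3% |

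These are ceilings on combination time, because a therapy need not be added and would start some time after NaF-3. Month 36 is the approximate duration of the whole study (Protocol 3.4), so it is an outer limit for any one patient. The data cutoff also limits it. The 30-day tail is left out.

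**Step 4: effect on an incidence.** One patient in 20 is 1/20 = 5.0 points. Suppose k patients add therapy, and each has probability q of a given event that the added therapy causes and that he would not otherwise have had. Expected inflation is 100·k·q/20 points. The chance of at least one such event is 1 − (1 − q)^k. Both k and q are assumptions:

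| k | q | Expected inflation (points) | Chance of at least one |
|---|---|---|---|
| 0 | any | 0 | 0 |
| 2 | 0.1 | 1.0 | 0.19 |
| 5 | 0.3 | 7.5 | 0.83 |
| 10 | 0.5 | 25.0 | 0.999 |

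**Step 5: the end day.** SAP 3.5, 6.5.6 and 6.6.1 run to the start of the listed therapy, whereas Protocol 10.4 stops the day before. The difference is at most one day per patient, or 20 patient-days in all. That is 1/85 = 1.18% of an 85-day window and 1/1096 = 0.09% of a 1096-day window.

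**The case against.** The strongest reply is that the gap is the protocol's own definition. Protocol 10.4 has the same closing list, a patient on combination therapy is still taking study drug, and counting his events as all-causality TEAEs is coherent. That stands. It is why the overall table should stay as defined: cutting it at the add-on date would discard genuine enzalutamide events.

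The treatment-related tables filter some add-on toxicity. The filter is partial, because Protocol Table 10 lets an event rated Possible also be explained by another drug, and SAP 6.6.1 counts a missing relationship as related. With about 20 patients, listings would allow events to be traced by hand, but that is not a planned summary.

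Several stronger readings are tempting but unsupported:

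- **The tables present combination events as monotherapy.** The SAP defines TEAEs by study-drug exposure and never labels the tables that way.
- **Deaths are affected.** SAP 6.6.3 tabulates all deaths and deaths within 30 days of last dose. It does not use this window.
- **Laboratory tables are already contaminated.** SAP 6.6.4 admits only central-laboratory results, while Protocol 8.4 and 12 place all safety tests in local laboratories. Read literally, there are no local results to tabulate, so the point applies only once that conflict is resolved.
- **First-day chemotherapy reactions are counted against enzalutamide.** The SAP has a rule for the first-dose day but none for the end day. Protocol 7.2 requires discontinuation and safety follow-up before such agents, and Protocol 8.3.2.1 stops collection before they start. Footnote 11 of Protocol Appendix 2 is looser, running up to initiation, but the matter remains one of wording.

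**Conclusion.** The concern holds for the all-causality TEAE tables. They pool events arising under enzalutamide alone with events arising after another anticancer therapy has been added, or has followed within 30 days, and no planned summary separates them. The gap originates in Protocol 10.4 and the SAP inherits it.

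The size cannot be determined, because the documents give neither the share of patients adding therapy nor the toxicity of what is added. What is firm is the granularity of 5 points per affected patient at N of about 20. The 1.0 to 25.0 point range illustrates the assumed k and q and is not an estimate. A reader might infer a definite upward bias in the reported incidences, but the documents show only that one is possible and would not be visible in the tables.

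The primary and secondary endpoints are imaging measures and are untouched. This is an inexpensive improvement to the safety reporting.

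**What to change.** 1. Keep the overall TEAE table on the window now in SAP 3.5.
2. Add a column or companion table split at the start date of the first added or subsequent systemic anticancer therapy or bone-targeting radionuclide. Assign events by onset date, and state the number of patients and the exposure time in each period. A patient can contribute to both periods, so the two counts need not sum to the overall count.
3. Take the start date from the recorded concomitant medications and treatments. State whether the SAP Appendix 1 rule for partial medication dates applies. It imputes to the first of the month or to 1 January, which moves the split earlier.
4. Reconcile SAP 6.6.4 with Protocol 8.4 and 12 on the laboratory source, then apply the same split to the laboratory shift tables.
5. Align the end day in SAP 3.5, 6.5.6 and 6.6.1 with Protocol 10.4, and say explicitly whether that day counts.

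The cost is SAP wording and one extra, possibly sparse, column. No new data are needed. If no patient receives such a therapy, one sentence in the study report replaces the column.
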